## **5.2. Enrolment (visit 1)**

At this visit, informed consent will be conducted face-to-face with the parent or legal guardian of the intended participant and the legal representative of the cord blood, either in person or by Skype or other video conferencing with the trial coordinator or a trial investigator. In most cases, because the intended participant and the cord blood donor must be full biological siblings they will have the same parent/guardian who is also the legal representative of the privately stored cord blood. Treating clinicians will not be able to take informed consent.

Participants will then give a blood sample for tissue typing to match with CBUs. The samples will be collected either by the pathology collection service at the infusion hospital or at a local pathology collection service, and then blood for tissue typing will be sent to the transplantation services division of the Australian Red Cross Blood Service appropriate to the participant's location. They will undertake generic HLA-A, HLA-B and HLA-DR (which are inherited together and called a haplotype; each genome has two haplotypes) matching with CBUs to confirm that the identified sibling CBU is a match with the participant. Note that if the generic testing of HLA reveals that both haplotypes match, i.e. 6/6, inheritance of HLA alleles as entire haplotypes means that 12/12 HLA alleles match but nevertheless we will conduct tissue typing to assess 12/12 HLA match. Tissue typing data will be received by a transplant physician at each site. If the CBU is a match, the transplant physician will order CBU pre-release work up from the CBB. ABO group and rhesus type will be checked at this time for participants who will receive sibling UCBCs, but incompatibility will not

prevent infusion. Sibling ABO group and rhesus type will be analysed from the CBU if sufficient red blood cells are available; otherwise it will be accepted from hospital records if available. If neither of these methods reveal the sibling ABO group and rhesus type, the sibling will need to attend the infusion hospital and provide a blood sample for testing.

If the participant has more than one HLA matched sibling CBU available, determining which is selected for the trial will rely on ABO Rhesus matching. The presence of multiple sibling CBUs in storage will be established prior to enrolment, and extra blood will be collected from the participant during visit 1 to determine the participant's ABO Rhesus group.

Both the participant and the sibling donor will need to provide saliva samples for genotyping prior to copy number deletion chimerism assays. These samples can be collected at the hospital or the trial coordinator can provide the family with collection kits which can be returned at visit 2.

### **5.3. Group allocation**

This study involves only a single group. If an individual participant has multiple eligible cord blood units in storage, a full matched sibling unit with matching ABO group will be selected as first preference and full matched sibling unit with mismatched ABO group as second preference.

Around 75% of enrolled participants will be excluded because their sibling UCBCs in storage are not a full match. These participants will be notified immediately, but participants with matched CBUs who are excluded due to a full treatment group will not be notified immediately because visit 2 involves further screening that may require replacement participants. Once all continuing participants have completed visit 2, excluded participants will be phoned by either the site PI or the trial coordinator to communicate their exclusion in the research study. At the conclusion of this study, we will send them a summary of results if they would like that.

Some children may have epilepsy given it is a common association with CP. Regardless of past history of epilepsy, participant families will be required to keep an epilepsy log to record frequency and severity of epileptic events to compare with a similar log after infusion (data collection form is attached).

Families will be referred to counselling services if they feel distressed by learning of their exclusion. Families may feel upset to learn that their child will be unable to use the cord blood unit in storage. Families may also be upset at the conclusion of the trial if they did not perceive any improvement during the trial.

### **5.4. Baseline (visit 2)**

Participants will be required to attend a second visit at the infusion hospital prior to infusion to confirm eligibility and establish baseline assessments. Participants will meet the trial doctors (both paediatrician and transplant specialist) to provide a medical history (including Appendix 10: Immunological screening questions) and undergo a physical examination including a photo of the participant's skin to record characteristic colouring and evidence of rash at baseline, the trial therapist who will conduct a CP assessment, and the therapist and a psychologist to establish baseline assessments. If clinical screening reveals a temporary issue, such as having a current infection, which may affect results of a screening immunology test, the participant may need to return to the hospital at an appropriate time in the future before continuing further.

The participant will then provide a blood sample at the hospital pathology collection service which will be used for confirmatory HLA typing (blood sent to Red Cross transplantation service for tissue typing of 6 HLA alleles), virology (blood sent to Red Cross Blood Service for nucleic acid test (NAT) HIV 1 & 2, anti-HIV 1 & 2 antibodies, Hepatitis B surface antigen, anti-Hepatitis B core antibody, NAT Hepatitis C virus, anti-Hepatitis C virus antibody, anti-Human T-lymphotropic virus 1 and 2 antibody and syphilis testing) and other pre-infusion screens through the hospital laboratory services to ensure the participant is otherwise healthy. The participant's immune-competence will be screened at this visit, with full blood examination, lymphocyte subsets, naïve T cells and immunoglobulins. The results will be interpreted along with the participant's clinical history and responses to the immunology screening questions. Trial doctors

will exclude from the study any participants suspected to have an immune deficiency disorder and refer them to the local clinical immunology team for further evaluation and management.

In some cases, it may be necessary to collect blood from the participant's mother, if Hepatitis B core Antibody (HepBcAb) was not tested from her blood at the time of cord blood collection, and depending on HepBcAb results from cord plasma sample tests. This allows a full risk assessment of HepB contamination. Clinically, HepBcAb positive cord blood that indicates a previous (maternal) exposure to HepB but no current infection would be eligible for use, however in this research context we cannot take even this minimal risk of contamination.

This visit must occur a minimum of five weeks after Visit 1, to allow time for HLA typing, the CBU order to go to the CBB and three weeks for a private CBB to complete release work up including contamination assessment on the CBU and transport of CBU to the cell therapy lab of the infusion hospital. The infusion hospital needs a minimum of three weeks between arrival of the CBU and infusion, to finalise release assessments. The virology and immunology screen during Visit 2 must occur between 10 and 30 days prior to infusion at Visit 3. Visit 2 will be scheduled accordingly.

### 5.5. Infusion (visit 3)

Following the confirmation of CP, participants will be invited for a third visit at the infusion hospital where they will undergo their infusion. All CBBs in Australia process cord blood to reduce volume, deplete the concentration of red blood cells and collect the buffy coat which includes all nucleated cells and a fraction of red blood cells (most of which lyse upon cryopreservation). There are minor differences in CBB protocols such as the designated minimum volume of cord blood and the minimum of total nucleated cells (TNC) in the cord blood eligible for storage. As far as possible, UCBC treatment will be kept uniform among participants. If a record search identified a CBU and the participant enrolled in the study, HLA type of the CBU will be compared with HLA type of the participant to ensure it is a 12/12 HLA match. AusCord CBUs have already been HLA typed and their records will be used; private CBBs will send a pilot sample of the CBU to the Red Cross transplantation service for HLA typing. If the CBU is correct, all CBBs will undertake a reference thaw if not already completed, to test the quality of the CBU and confirm tissue type. Next, the transfusionist will organise CBU transport to the infusion hospital cell therapy lab where it will be stored below -180°C in the vapour phase of liquid nitrogen. On the day of infusion, lab staff will thaw the CBU and then wash by diluting in dextrose/albumin and centrifuging to collect cells to minimise the presence of DMSO cryopreservant (less than 1% DMSO remains, an undetectable scent). The infusion hospital labs will report on post-thaw CBU qualities after release, including TNC, cell viability, CD34+ cell count, aerobic and anaerobic contamination and supernatant haemoglobin (see section 7 for details).

Upon arriving at the infusion hospital day medical facility on the day of the infusion, the participant will provide a blood sample to the research nurse. This sample will have DNA, RNA and serum proteins extracted to compare with CBU and with post-infusion blood.

Cannulation      A peripheral vein catheter (PVC) will be inserted in the foot, hand or antecubital fossa after application of a numbing cream.

Age range	Gauge of PVC
Infants and toddlers	24 – 22
Older children	22 – 20

Hydration:      All participants will receive intravenous hydration, starting 2 hours prior to infusion and continuing for 4 hours after the conclusion of the infusion. This is to ensure good clearance of any residual red blood cells and free haemoglobin following infusion. Hydration will continue until urine is clear and there is no indication of hypertension. 0.9% NaCl (normal saline)  
125 mL/m^2/hr for a total of 6 hours  
Ordered by transplant physician or delegate  
Infused by nurse

Pre-Medication Ordered by transplant physician or delegate  
Administered by nurse

Medication	Administration	Timing	Reason
Hydrocortisone 25-100 mg	Intravenous	2 hours prior to infusion	To prevent allergic reaction
Antihistamine*	Oral or intravenous	1 hour prior to infusion	To prevent allergic reaction
Paracetamol	Oral	1 hour prior to infusion	Pain prevention
Ondansetron	Oral	1 hour prior to infusion	Nausea prevention

\* The antihistamine will be selected according to clinical indication. Promethazine (Phenergan), which has sedative properties, may be used for children with saliva and airway control, but if there is concern about the airway cetirizine (Zyrtec) or other antihistamines may be used.

Infusion: Intravenous (foot, hand or antecubital fossa)  
Catheter size as above (compromise between smallest being easiest for children, whilst remaining large enough to prevent cell damage)  
Infused over the course of 10-20 mins depending on age of the participant  
Maximum volume of infusate is 10 mL/kg recipient  
Ordered by transplant physician or delegate  
Infused by nurse  
Additional infusion identity check by study staff

Minimum TNC: > 1 x 10^7 cells/kg body mass (in line with other international trials)

In the case of a Rh+ donor and Rh- recipient, the transfusionist or transplant physician will order anti-Rhesus D immunoglobulin (Anti-D) from the hospital blood bank, which will be delivered by i.v. or i.m. injection 24 hours after infusion (at visit 4) to prevent development of antibodies. The Anti-D administration is precautionary, the red blood cell depletion of CBUs and lysing of remaining red blood cells during cryopreservation combined with the CBU washing procedure means there should be negligible red blood cell antigens (ABO, rhesus, Kell or others) remaining.

All participants will be observed carefully by the nurse following the infusion (see section 7) with a transplant physician available if observations fall outside the normal range (see section 8). Blood will be collected by the nurse 1 hour after conclusion of infusion to compare with baseline.

Participants will be released from the hospital if they are haemodynamically stable and do not have haemoglobinuria. Participants will return to the hospital the next day for a physical examination and blood test. If there is any indication of infection or serious adverse event, the participant may need to remain in hospital for observation or medical attention. This is not expected. Participants will be provided with emergency phone numbers and instructions (see Appendix 11: Post-infusion handout).

Further blood samples will be taken at 1 week, 1 month and 3 months, for both research and safety reasons (see Table 1).

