## 6. STUDY VISITS AND PROCEDURES SCHEDULE

Study phase	Enrolment	Baseline	Infusion	Follow up					
Visit number	1	2	3	4	5	6	7	8	9
Timing	> 8 wks prior to infusion	21 days prior to infusion	0	1 day	1 wk	1 mo	3 mo	6 mo	12 mo
Tolerance	Any time	> 3 wks since Visit 1	- Within 10-30 days of clear virology screen - CBU available	± 0 days	±2 days	± 7 days	± 2 wks	± 2 wks	± 2 wks
Location	Hospital	Hospital	Hospital	Hospital	Hospital, home	Hospital	Hospital	Hospital, community	Hospital
Informed consent (45 mins)	X								
CP assessment (30 mins)		X							
Medical history (0.5 hr)		X							
Physical examination (0.5 hr)		X	X	X		X	X	X	X
Medical assessment (10 mins)				X	X	weekly	X	X	X
Assessment of motor function (45 mins)		X					X		X
Assessment of upper limbs (15 mins)		X					X		X
Assessment of quality of life (0.5 hr)		X					X		X
Assessment of cognition (2hr 15)		X							X
Infusion of UCB (30 mins)			X						
Intravenous fluids, observation (6 hrs)			X						
Anti-D administration if required (5 mins)				X					
Blood collection	X	X	2X	X	X	X	X		
Rehabilitation Therapy									
Length of visit	1 hr	6 hrs (may need two visits)	9 hrs	1 hr	1 hr	1 hr	2 hrs	1 hr	4 hrs

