#### Observation

Vital signs will be monitored by the nurse prior to UCBC infusion, during the infusion, every 15 minutes for 1 hour, then every 30 minutes for 2 hours. The monitoring will include temperature measurement (in °C), blood pressure (in mmHg), pulse oximetry (in % oxygen saturation) and checks for nausea and discomfort.

Participants will also be monitored for symptoms of toxicity, including nausea, fever, chills, and for symptoms of anaphylaxis including wheezing and urticaria.

A transplant physician will be available and called if vital signs fall outside the normal range (see section 8) or if there are signs of an adverse event.

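### As worded, the hydration rule in section 5.5 keeps saline running in a child whose urine is clear but whose blood pressure is raised

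*Protocol*

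**What the plan says.** The Hydration paragraph of Protocol section 5.5 gives every participant intravenous normal saline, "starting 2 hours prior to infusion and continuing for 4 hours after the conclusion of the infusion". The rate is 125 mL/m²/hr "for a total of 6 hours", ordered by the transplant physician or a delegate and given by a nurse. The schedule in section 6 also allots 6 hours to fluids and observation.

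The paragraph states its purpose: "This is to ensure good clearance of any residual red blood cells and free haemoglobin following infusion". It then gives a condition for ending the fluid: "Hydration will continue until urine is clear and there is no indication of hypertension".

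Later in section 5.5 there is a separate rule for discharge: "Participants will be released from the hospital if they are haemodynamically stable and do not have haemoglobinuria".

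**The concern.** The closing condition joins two requirements with 'and'. Fluid ends only when urine is clear and, in addition, there is no sign of hypertension. The first requirement follows from the clearance purpose. The second does not: once urine is clear, raised blood pressure is no reason to give more saline, and it would ordinarily prompt a check on whether to give less. Appendix 13 itself lists pulmonary oedema as a possible sign of transfusion-associated circulatory overload, so the authors had fluid overload in view.

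This is an instruction to be carried out at the bedside, in a trial open to children aged 1 to 16 years. What is at stake is whether a nurse or delegate reading the sentence as written would take the right action in a child whose pressure is raised.

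**Working it through.** **The planned course.** Inputs from section 5.5: 2 hours before, 4 hours after, 125 mL/m²/hr.

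- Duration: 2 + 4 = 6 hours, which reproduces the stated total (the 10 to 20 minutes of cell infusion are not counted).
- Volume: 125 × 6 = 750 mL/m², of which 125 × 2 = 250 mL/m² is before the infusion and 125 × 4 = 500 mL/m² after it.

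The planned course is therefore coherent. The rate is tied to the 6 hours and none is given for any extension, so the volume of an extension cannot be derived from the document.

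**The condition, read three ways.** Literally, stop = (urine clear) AND (no hypertension), so continue = (urine not clear) OR (hypertension). Two other readings are plausible: a proviso (continue until urine is clear, provided there is no hypertension), or a slip in which 'hypotension' was meant. At the end of the planned course they give:

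| Urine | Blood pressure | Literal | Proviso | 'Hypotension' meant |
|---|---|---|---|---|
| Clear | Normal | Stop | Stop | Stop |
| Not clear | Normal | Continue | Continue | Continue |
| Clear | Raised | **Continue** | Stop | Stop |
| Not clear | Raised | Continue | Do not continue | Continue |
| Clear | Low | Stop | Stop | Continue |

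All three agree when pressure is normal. They part when it is raised or low. In the third row only the literal reading continues fluid, and there it serves no clearance purpose.

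**Whether another part of the protocol corrects it.**

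- *Discharge rule, section 5.5.* It governs when the child leaves hospital, not when fluid stops. A child with unstable pressure would be kept in, but the rule does not say what to do with the saline.
- *Observation, section 7.1.* Blood pressure is named among the vital signs, with checks every 15 minutes for 1 hour and then every 30 minutes for 2 hours. A transplant physician is called for values outside the normal range, with a pointer to section 8.
- *Section 8.* It adds 30-minute monitoring during hydration and refers to Appendix 13 for severity grades. It gives no instruction on fluid.
- *Appendix 13, Hypertension.* It grades severity, and some grades mention medical intervention. It does not direct the saline.

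These provisions would bring raised pressure to a physician's notice. None tells staff to slow or stop the fluid, and none overrides the sentence in section 5.5.

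**The case against.** The strongest reply is that no competent team would follow the sentence literally. A transplant physician or delegate orders the fluid, blood pressure is measured, a physician is on call, and the literal reading is the least plausible of the three. This stands as an argument about likelihood, and it is why the point is minor. It does not make the sentence right: the two sensible readings call for different actions when pressure is low, or when it is raised with urine not yet clear, and the text does not choose between them.

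A reader might go further and infer that section 5.5 contains two competing rules for duration, a fixed 6 hours and an open-ended condition, with no limit on the second. The document does not support that. The paragraph reads naturally as a sequence: a 6-hour ordered course, continued if urine has not cleared. The discharge requirement of no haemoglobinuria fits this, and the 6 hours in the schedule is a planned time rather than a rival stopping rule. Leaving the length of an extension to the ordering physician is ordinary clinical discretion. The 10 mL/kg ceiling elsewhere in section 5.5 is for a cell product given over 10 to 20 minutes and sets no standard for hydration.

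A reader might also put a figure on the excess fluid, for example 125 mL/m² for each extra hour. That assumes the planned rate continues after 6 hours, which the protocol does not say, and the protocol gives no expected frequency of extension.

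**Conclusion.** The hypertension condition is wrong as written. Taken literally it prolongs saline in a child with clear urine and raised blood pressure, for no purpose the protocol states, and no other section corrects it. That much follows from the text alone. That it is a drafting slip is an inference, though a likely one.

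The consequence is small. It concerns only a child whose pressure is raised at the point when fluid would otherwise end, and existing ordering, monitoring and call-out arrangements make harm unlikely. The documents do not support a claim that children would in fact be overloaded, nor any estimate of volume or frequency. No endpoint, sample size, stopping rule or analysis is affected. It is a minor safety correction, worth making because this is an operative instruction for treating children.

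**What to change.** Replace the sentence in section 5.5 with wording to this effect: hydration runs for the planned 6 hours (2 hours before and 4 hours after the infusion); it is extended only if urine is not clear, on the transplant physician's order; if blood pressure is raised for the child's age, slow or stop the fluid and call the transplant physician. If 'hypotension' was intended, correct the word instead, which also removes the literal problem.

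The cost is a short rewording of one paragraph, a clinical decision on what counts as raised for age, and whatever ethics approval a protocol amendment needs. No procedure, visit or data item is added.

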**Table 1: Details of all proposed blood samples**

Blood collection	Volume	When is it taken?	What is it for?	Where does it go?	What happens to it afterwards?
1	9 mL; Blood spot	Soon after enrolment	- Low resolution HLA typing to match sibling or autologous CBU with participant - Immunology screening	- Red Cross Transplantation Services - RCH Melbourne Immunology Lab*	Transported, destroyed

Sibling sample	2.7 mL	Soon after enrolment (only if assay cannot be conducted on CBU)	- To assess blood group and rhesus type	- Infusion hospital labs	Transported, destroyed
Maternal sample	2.7 mL	3 weeks prior to infusion (if not previously conducted)	- To assess HepBcAb (to assess risk of HepB contamination of cord blood)	- Infusion hospital labs	Transported, destroyed
2	9 mL 7 mL	3 weeks prior to infusion	- Low resolution confirmatory HLA typing to ensure matching blood is used - To assess blood group and rhesus type - To assess health of participant	- Red Cross Transplantation Services - Infusion hospital labs	Transported, destroyed
3	4 mL 7.2 mL	2 hours before infusion	- To compare with the blood sample taken after treatment	- Cell therapy lab - Infusion hospital labs - Cyto-molecular diagnostics lab* - Research labs*	Frozen, transported and stored
4	8.2 mL	4 hours after infusion	- To look for inflammation - To compare with blood taken at baseline	- Infusion hospital labs - Cyto-molecular diagnostics lab* - Research labs*	Frozen, transported and stored
5	8.2 mL	24 hours after infusion	- To check for infection - To check the cell types in the participant's blood	- Infusion hospital labs - Cyto-molecular diagnostics lab* - Research labs*	Frozen, transported and stored
6	8.2 mL	1 week after	- To look for inflammatory markers, signs of GvHD - To check the cell types in the participant's blood	- Infusion hospital labs - Cyto-molecular diagnostics lab* - Research labs*	Frozen, transported and stored
7	6.4 mL	1 month after	- To check the cell types in the participant's blood, chimerism assessment - To look for inflammatory markers, signs of GvHD	- Infusion hospital labs - Cyto-molecular diagnostics lab* - Research labs*	Frozen, transported and stored
8	6.4 mL	3 months after	- To check the cell types in the participant's blood, chimerism assessment - To look for inflammatory markers, signs of GvHD	- Infusion hospital labs - Cyto-molecular diagnostics lab* - Research labs*	Frozen, transported and stored

\* Centralised testing, involving sample transport to Melbourne. RCH Melbourne Immunology Labs will undertake first line immunology screening; MCRI Cyto-molecular Diagnostics Lab will undertake chimerism assays.

